10.1 Disposition of Participants and Discontinuations

The number and percentage of participants in each of the below disposition categories will be presented based on the electronic case report form (eCRF) data. Percentages will be presented with respect to the number of treated participants

- Total number of participants screened (i.e. participants who gave informed consent)
- Number of participants who discontinued from the study prior to study intervention overall and grouped by the main reason (e.g. the failed specific inclusion or exclusion criteria, adverse event, lost to follow-up, death, progressive disease, withdrawal of consent and other)
- Number of re-screened participants
- Number of participants who received at least one dose of study intervention (FAS/SAF analysis set)
- Number and percentage of participants with treatment ongoing at the data cut-off date
- Number and percentage of participants off study treatment, grouped by main reason (treatment completed as per protocol, progressive disease, death, adverse event, lost to follow-up, protocol non-compliance, withdrew consent, other)
- Number and percentage of participants who reinitiated the study treatment and number of participants who discontinued the study intervention after reinitiation
- Number and percentage of participants with treatment ongoing at the end of study
- Number and percentage of participants who completed/discontinued the study participation, with the associated main primary reason (study completed according to protocol, adverse event, lost to follow-up, protocol non-compliance, death, withdrew consent, other)

In addition, the number of participants screened, and enrolled in each analysis population defined in Section 8.2 will be summarized, overall and by region (North America, Europe, South America, Asia, RoW), by country within region and by site. Subject disposition and analysis sets may be repeated for China and Japan sub-populations.

The listing of participant disposition will include all participants (i.e. including screening failures, but not re-screened participants (at their screen failure time) which will be listed in a specific listing). The listing will include the following information: participant identifier, date of informed consent, included in the study (if not reason for exclusion), first/last study intervention date, date and reason off-treatment, date and reason off-study, population flags. When the reason such as

reason off-treatment will be categorized as “Other, specify” or “Withdrew consent from treatment, specify”, the verbatim text as entered in the eCRF will be presented in the listing.

In addition, a listing of participants for which study treatment has been reinitiated will be provided with the following information: participant identifier, date of first study intervention, date of last study intervention, reason for treatment termination, first and last reinitiation study treatment administration date and status at end of treatment reinitiation including reason for treatment discontinuation, as applicable.

If any re-screened participants are observed, they will be presented in a specific listing which will include: participant identifier (identifier at inclusion in the study), date of informed consent at inclusion, date of first study treatment, initial participant identifier (identifier at screen failure), date of informed consent at screen failure, date and reason of screen failure. Note in case participants have been screened several times, all screening attempts will be listed.

In addition, for the assessment of COVID-19 impact on this study, a listing will include the following information (as applicable): participant identifier, date of first and last dose, pandemic start date in the country, if treatment period was potentially affected by pandemic, if any COVID-19 related AE or PD occurred during the pandemic period.

10.2.2 Reasons Leading to the Exclusion from an Analysis Population

Reasons for exclusion from the PKAS will be provided in table(s)/listing(s).

11 Demographics and Other Baseline Characteristics

Analysis Set: FAS

Demographics medical history and other baseline characteristics may be repeated for China and Japan sub-populations.

11.1 Demographics

Demographic characteristics and physical measurements will be summarized descriptively using the following information from the Screening/Baseline Visit eCRF pages.

The following demographic characteristics will be included:

- Sex: female
- Ethnicity: Hispanic or Latino, not Hispanic or Latino
- Race:
 - For participants reporting one race only: White, Black or African American, Asian Indian, Chinese, Filipino, Japanese, Korean, Vietnamese, Other Asian, American

Indian or Alaska Native, Native Hawaiian or other Pacific Islander, Not collected at the site, Other.

- For participants reporting multiple races, all combinations will be reported under ‘More than one race’ category.
- Age (years)
- Age categories
 - < 65 years, ≥ 65 years
 - 18-49 years, 50-64 years, 65-74 years, 75-84 years, ≥ 85 years
- Pooled Region
 - North America
 - Europe
 - South America
 - Asia
 - RoW

Specifications for computation:

- Age [years]: $(\text{date of given informed consent} - \text{date of birth} + 1) / 365.25$
The integer part of the calculated age will be used for reporting purposes.
- Site codes will be used for the determination of the participant’s geographic region.

This summary table will also be repeated to evaluate subjects split by prior Bevacizumab used or not, and may be repeated for Japanese status (Japanese, non-Japanese, all).

Demographic characteristics including participant identifier, sex, race (including all reported races in case of “multiple” races, and details in case of “other” race), ethnicity, geographic region, age (years and category), height, weight and body mass index (BMI) at baseline will be presented in a listing.

11.2 Medical History

Relevant past and ongoing medical conditions at baseline will be summarized from the “Medical History Details” eCRF page, using the latest available version of Medical Dictionary for Regulatory Activities (MedDRA) at the time of the database lock, preferred term (PT) as event category and MedDRA system organ class (SOC) body term as Body System category.

Medical history will be displayed in frequency tables, ordered by primary SOC and PT in alphabetical order. Each participant will be counted only once within each PT or SOC. Categories for Human immunodeficiency virus (HIV) infection, Multi-drug resistance preventing effective antiretroviral therapy, Multi-drug resistance not preventing effective antiretroviral therapy and Aids defining opportunistic infection will be also displayed in a separate table.

Listing of medical history including participant identifier, age, sex, race, PT, reported medical history term, start/end dates, related study condition, ongoing at screening and toxicity grade (when medical history is ongoing) will be presented.

11.3 Other Baseline Characteristics

11.3.1 Disease History

Information on disease characteristics collected on the “Disease History” eCRF page will be summarized as follows:

- Tumor histology: Squamous cell carcinoma, Adenocarcinoma, Adenosquamous cell carcinoma, Other
- Time since initial cancer diagnosis (months)
- Time since documented, locally advanced, inoperable or metastatic disease (months)
- Time since last progression of disease prior to study entry (months)
- TNM classification at initial diagnosis: each T, N, M category will be described (TX, T0, N1, etc.)
- MSI status: High, Low, MSS, Unknown. MSI status will be centrally determined by means of the Tumor tissue sample at Baseline and will be provided as external data

This summary table will also be repeated to evaluate subjects split by prior Bevacizumab used or not, and may be repeated for Japanese status (Japanese, non-Japanese, all).

Listing will also be provided with the following information:

- Participant identifier, age, sex, race, tumor histology, date of initial cancer diagnosis (months), date of documented, locally advanced, inoperable or metastatic disease (months), date of last disease progression (months), TNM classification at initial diagnosis and MSI status

11.3.2 HPV test

HPV testing history as collected on the “Disease History” eCRF page and HPV status retrospectively measured from central testing will be summarized respectively by the frequency and percentage of participants having the following history of:

- HPV16+ or HPV18+, HPV+ (all other subtypes), HPV-, or NA
- High risk HPV+ (if HPV 16, 18, 31, 33, 35, 39, 45, 51, 52, 56, 58, 59, 66, or 68 is positive), Low risk HPV+ (if subject is positive for any other HPV subtype than the ones listed on high risk), HPV- (if none of HPV subtypes are detected), or Not done (if result is not reported).

For data coming from eCRF, as they are several possibilities of testing (tumor, pre-malignant cervical lesion and other), it will be enough for a participant to have one positive value, HPV16, HPV18 or in another subtype, in one of the three possible tests to be in the associated subgroup.

This summary table may be repeated for Japanese status (Japanese, non-Japanese, all).

Listing will also be provided and include: participant identifier, age, sex, race, visit, testing date, location, test source, kit used and HPV status of tumor and pre-malignant lesion or other history of HPV positive testing. Tissue sample collection date will be also provided for data coming from central lab.

11.3.3 PD-L1 test

Programmed Death-ligand 1 (PD-L1) expression will be collected from two different sources, eCRF page and external data coming from tests conducted by central lab.

All tests collected on the “PD-L1 Tumor Testing” eCRF page will be summarized. This includes 22C3, SP142, SP263, Dako 28-8, Dako 73-10 and other testing. All tests will be described using the following categories: positive, negative, NE or NA except Dako 28-8 which will use the following categories: < 1%; >= 1%; >= 5%; >= 10%, NE or NA.

In addition, PD-L1 expression as collected from central lab testing will be described using the following categories:

- PD-L1 expression in tumor tissue measured by 22C3 (CPS >= 1, < 1, NE or NA)
- PD-L1 expression in tumor tissue measured by SP263 (vCPS >= 5%, < 5%, NE or NA)

This summary table will also be repeated to evaluate subjects split by prior Bevacizumab used or not, and may be repeated for Japanese status (Japanese, non-Japanese, all)

Listing will also be provided and include: participant identifier, age, sex, race, unique sample identifier, visit, sample collection date, date of PD-L1 testing, method of testing, manufacturer/qualified pathologist reported result, raw value for the central lab testing and PD-L1 expression status.

11.3.4 Vital signs at Baseline

The following vital signs at baseline will be collected from the “Vital signs” eCRF page and will be summarized:

- Height (cm)
- Weight at baseline (kg)
- Body Mass Index (BMI) (kg/m²)

Specifications for computation:

$$\text{BMI (kg/m}^2\text{)} = \text{weight(kg)/[height(m)]}^2$$

Height, weight and BMI at baseline will be listed in the demographics listing (see Section 11.1).

Other vital signs parameters such as systolic and diastolic blood pressure, pulse rate and respiration rate at baseline will be included in the summary tables by timepoint.

11.3.5 ECOG Performance Status at Baseline

The ECOG Performance Status will be described from the data collected on the “ECOG Performance Status” eCRF page. It will be described at baseline by the frequency and percentage of participants in each category:

- 0: Fully active, able to carry on all pre-disease performance without restriction.
- 1: Restricted in physically strenuous activity but ambulatory and able to carry out work of a light or sedentary nature, e.g., light house work, office work.
- 2: Ambulatory and capable of all selfcare but unable to carry out any work activities. Up and about more than 50% of waking hours.
- 3: Capable of only limited selfcare, confined to bed or chair more than 50% of waking hours.
- 4: Completely disabled. Cannot carry on any selfcare. Totally confined to bed or chair.
- 5: Dead.

11.3.6 Skin status history

Skin status history is collected on the “Skin Status History” eCRF page and will be summarized by the frequency and percentage of participants having the following history of:

- Frequent sunburn (Yes, No, Unknown)
- Easy sunburn (Yes, No, Unknown)
- Skin cancer (Yes, No, Unknown)
- Significant UV exposure (Yes, No, Unknown)
- Photosensitivity due to skin disorder (Yes, No, Unknown)
- Photosensitivity due to medication (Yes, No, Unknown)
- Family history of skin cancer in first degree relative (i.e. parents, siblings and/or children) (Yes, No, Unknown)
- Number of participants having history of the skin conditions above (No condition, 1 condition, 2 conditions, 3 or more conditions)

A listing of skin status history will be provided.

CCI

CCI

12 Previous or Concomitant Medications/Procedures

Analysis Set: FAS

The tables in this section may be repeated for China and Japan sub-populations.

12.1 Previous and concomitant medications

Concomitant treatments are medications, other than study treatment, which are taken by participants any time during the on-treatment period, see Section 9.8. All medications starting the same day as study drug will be considered as concomitant. Medications starting 30 days after the last dose of study treatment will also be considered as concomitant.

Previous medications are medications, other than study treatment and pre-medications for study treatments, which started before first administration of study treatments.

A medication may be classified as both concomitant and previous. The respective flags will be derived based on start and end date.

Concomitant and previous treatment each will be summarized by number and percentage of participants from the “Concomitant Medication Details” eCRF. ATC-2nd level and PT will be tabulated as given from the WHO-DD dictionary most current version at the time of the database lock. If any previous or concomitant medication is classified into multiple ATC classes, the medication will be summarized separately under each of these ATC classes. The summary tables will be sorted by decreasing frequency of drug class and decreasing frequency of drug name in a given drug class. In case of equal frequency regarding drug class (respectively drug name), alphabetical order will be used. In case any specific medication does not have an ATC classification level 2 coded term, it will be summarized under “Unavailable ATC classification” category. Each participant will only be counted once, even if he/she received the same medication at different times.

Specific rules will be used to define if a medication/procedure is considered as a previous, concomitant or both previous and concomitant medication/procedure as detailed in Section 9.9.

Previous and concomitant medications will be presented in listing and include: participant identifier, age, sex, race, PT, medication name as provided by the Investigator, start date, end date, dose, dose units, frequency, route, reason for the medication.

12.2 Premedications prior to bintrafusp alfa administration

Premedications are medications administered per protocol on the same day as, but prior to, the study intervention to mitigate potential infusion-related reactions.

As per protocol, premedication prior to bintrafusp alfa administration for the first two infusions is optional and at the discretion of the investigator. If Grade 2 or more infusion reaction(s) are seen during the first 2 infusions, premedication should be continued/implemented for future infusions.

If at least 10 participants received premedication during the study, the number of participants receiving premedication will be summarized for each treatment visit based on “Premedication Bintrafusp Alfa Details” eCRF page. Percentages will be calculated on the number of participants who received an infusion at the associated visit.

Listing will be provided including: participant identifier, age, sex, race, medication name, visit, date/time of study intervention, dose, dose units, and route.

12.3 Concurrent procedures

Concurrent procedures are reported according to the “Concomitant Procedures Details” eCRF page.

Listing will be provided including: participant identifier, age, sex, race, name of procedure (as provided by the Investigator), start date, end date, indication, reason for procedure and type of specimen collected. A flag will be displayed to identify each procedure as prior to treatment and on-treatment.

12.4 Previous anticancer treatments and procedures

The previous anticancer treatments and procedures are collected under the “Prior Anti-Cancer Drug Therapies Details” and the “Prior Anti-Cancer Surgeries Details” eCRF pages.

The number of participants in each of the following anticancer treatment categories will be tabulated:

- Participants with at least one type of previous anticancer treatment or procedure (i.e. drug therapy, radiotherapy or surgery)
- Participants with at least one previous anticancer drug therapy
- Participants with at least one radiotherapy
- Participants with at least one previous anticancer surgery
- Participants with at least one previous Concurrent Chemoradiation Therapy (CCRT)

Following details for previous systemic anticancer drug therapy will also be summarized:

- Number of any previous anticancer therapy regimens: 0 / 1 / 2 / 3 / ≥ 4
- Number of prior lines of therapy for metastatic/locally advanced disease: 0 / 1 / 2 / 3 / ≥ 4
- Number of prior lines of therapy for metastatic/locally advanced disease excluding CCRT: 0 / 1 / 2 / 3 / ≥ 4
- Intent of therapy: Neoadjuvant / Adjuvant / Metastatic or Locally advanced

- Best response of last treatment regimen: Complete Response (CR) / Partial Response (PR) / Stable Disease (SD) / Progressive Disease (PD) / Non-Complete Response/Non-Progressive Disease (non-CR/non-PD) / Not Evaluable / Unknown.

Please note that radiotherapies taken alone will not be considered as a line of therapy

Previous anticancer drug therapies and radiotherapies and previous anticancer surgery will be presented in separate listings:

- The previous anticancer drug therapies and radiotherapies listing will contain participant identifier, age, sex, race, regimen ID, PT, medication name, start date, end date, intent of therapy, best response, date of progression. Radiotherapy administered as part of previous drug therapy with start date, end date, total dose, number of fractions and location will also be displayed.
- The previous anticancer surgery listing will contain participant identifier, age, sex, race, date of surgery, name and location of surgery, curative intent of surgery (Y/N), and outcome of surgery.

12.5 Previous pre-cancerous procedures of the cervix

The previous pre-cancerous procedures of the cervix are collected under the “Previous Pre-cancerous Procedures of the Cervix Details” eCRF page.

Previous pre-cancerous procedures will be presented in a listing which will include participant identifier, age, sex, race, name of procedure (as provided by the Investigator), start date, end date, indication and reason for procedure.

12.6 Subsequent anticancer treatments and procedures

Anticancer treatment after discontinuation of study drug will be summarized according to the eCRF page "Anti-cancer Treatment After Discontinuation" for anticancer drug therapy, "Radiotherapy After Discontinuation" for anticancer radiotherapy and to "Surgery After Discontinuation" for anticancer surgery.

The number of participants in each of the following anticancer treatment categories will be tabulated:

- Participants with at least one subsequent anticancer treatment (i.e. drug therapy, radiotherapy or surgery)
- Participants with at least one subsequent anticancer drug therapy
- Participants with at least one subsequent anticancer radiotherapy
- Participants with at least one subsequent anticancer surgery

If collected in the eCRF, the best response of first subsequent anticancer drug therapy will also be described (Complete Response (CR) / Partial Response (PR) / Stable Disease (SD) / Progressive

Disease (PD) / Non-Complete Response/Non-Progressive Disease (non-CR/non-PD) / Not Evaluable / Unknown).

In addition, the anticancer treatment after discontinuation of study treatment will be provided in two listings:

- For medication: participant identifier, age, sex, race, PT/medication name, regimen name, start date, end date, route and best response (if collected in the eCRF)
- For radiotherapy and surgery: participant identifier, age, sex, race, start date, end date, radiotherapy site or name of surgery/location, if surgery outcome and was the surgery curative in intent (Y/N)

13 Study Treatment: Compliance and Exposure

Analysis set: SAF

The tables in this section may be repeated for China and Japan sub-populations.

Participants will be treated with bintrafusp alfa at a dose of 1200 mg once every 2 weeks, until confirmed progression of disease (PD), death, unacceptable toxicity, study withdrawal, or up to 24 months.

All dosing calculations below and summaries will be based on “Bintrafusp Alfa Administration Details” eCRFs page. Data collected during the treatment reinitiation phase will be included in the summary statistics and described in listings.

For the analysis of exposure, a dose is regarded to be administered if the actual dose received is > 0 mg.

Imputation for incomplete start and end dates of study treatments are described in Section 9.9.

The **duration** of treatment of bintrafusp alfa (in weeks) during the study is defined as:

$$\text{Duration of treatment} = \left(\frac{\text{date of last dose} - \text{date of first dose} + 14}{7} \right)$$

The **cumulative dose** overall of bintrafusp alfa per participant is the sum of the actual dose that the participants received during the study (i.e., total dose administered (mg)).

The **dose intensity** of treatment (DI) (mg/cycle) of bintrafusp alfa during the study is defined as

$$\text{DI of treatment} = \left(\frac{\text{Cumulative dose of treatment (mg)}}{\text{Duration of bintrafusp alfa of treatment (in weeks)/2}} \right)$$

The **relative dose intensity** (RDI) is defined as the actual dose intensity divided by the planned dose intensity during the study and expressed in percentage:

$$\text{RDI of treatment (\%)} = 100 \times \left(\frac{\text{DI of treatment (mg/cycle)}}{\text{planned dose (mg/cycle)}} \right)$$

Where the planned dose is 1200 mg/cycle

The following summary tables will be provided:

- Duration of therapy (weeks)
- Total number of infusions received
- Cumulative dose (mg)
- Dose intensity (mg/week)
- Relative dose intensity (%) as continue variable, and categorized as
 - < 80%
 - 80%-90%
 - > 90%

Duration of therapy and cumulative dose, dose intensity and relative dose intensity tables may be repeated by Japanese status (Japanese, non-Japanese, all).

Two listings will be presented:

- A listing of study intervention which will provide: participant identifier, age, sex, race, visit, infusion start date and time, infusion end date and time, infusion rate (mL/hr), actual dose (mg), route, administration modification and reason for modification, change in administration detail, treatment delay (days). Data collected during the treatment reinitiation phase will be flagged.
- An additional listing of treatment exposure and compliance which will include participant identifier, age, sex, race, duration of therapy (weeks), total number of infusions received, cumulative dose of therapy (mg), dose intensity (mg/week), and relative dose intensity (%).

Dose Modification

Dose modification is not allowed per protocol. No summaries will be provided.

Therapy Delays

Delays of therapy will be derived for each infusion as the number of days since last infusion – 14:

Therapy Delays = start date of current infusion – start date of the previous infusion – 14

If the result is > 0 day, then this will be classed as a delay. A participant may have more than one treatment delay throughout the course of treatment.

The following will be summarized in a table:

- Number of participants with at least one delay
- Number of participants with no delay
- Number of delays per participant (0 delay, 1 delay, 2 delays, 3 delays, ≥ 4 delays)
- Longest delay per participant (no delay, 1-2 days, 3-8 days, 9-15 days, ≥ 16 days)

Infusion Temporary Interruptions

Study drug infusion temporarily interrupted as recorded on the “Study Treatment Administration Details” page of the eCRF will be used for analysis. Number of participants with at least one study drug temporary interruption, reason for study drug temporary interruption (adverse event or other), as well as a categorization of the number of study drug temporary interruptions (1 / 2 / ≥ 3) will be summarized.

Infusion Rate Reductions

Infusion rate reductions as recorded on the “Study Treatment Administration Details” eCRF page will be used for analysis. Number of participants with at least one infusion rate reduction, reason for infusion rate reductions (adverse event or other), as well as a categorization of the number of infusion rate reductions (1 / 2 / ≥ 3) will be summarized.

14 Efficacy Analyses

Analysis Set: FAS

14.1 Primary Endpoint: Confirmed objective response according to RECIST 1.1 as adjudicated by IRC

Primary endpoint is the confirmed objective response according to Response Evaluation Criteria in Solid Tumors Version 1.1 (RECIST 1.1) assessed by an IRC.

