7.1.2 Rechallenge

7.1.2.1 Reinitiation

One reinitiating course of treatment at the same dose and schedule and treatment duration up to 24 months is allowed at the discretion of the Investigator and agreement of the Medical Responsible for:

- Participants who are experiencing SD, a PR, or CR at the time of discontinuation, and then subsequently develop disease progression after stopping therapy, but prior to the End of the Study.

OR

- Participants who are discontinued due to an AE that is subsequently well managed or resolved after stopping therapy, but prior to the End of the Study.

The participant should reinitiate treatment at the treatment phase visit where they left off according to the SoA (see Table 1). Participants who reinitiate treatment should stay on study and should be treated and monitored according the SoA for the rest of the study.

Prior to reinitiation, the Investigator will need to confirm that the benefit of reinitiating treatment outweighs any risk involved, such as that which led to initial treatment discontinuation. For participants with only stable disease at the time of discontinuation, the Investigator should confirm that no other reasonable treatment options are available. In addition, to be eligible for reinitiation, the participant must not have previously withdrawn consent for this trial and should have been followed up with regular eCRF documented evaluation scans up to reinitiation of treatment.

A rebaseline scan must be performed prior to reinitiation of study treatment. Additionally, relevant safety laboratory assessments, including both full hematology and full chemistry results within 2 weeks, must be available and verified. The clinical Investigator will determine whether additional evaluation and work-up are required on a case-by-case basis. A discussion with the study team is warranted to determine whether PK/CCI testing is indicated upon restarting treatment.

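### For participants who reinitiate treatment, the SAP's exposure formulas count the off-drug gap between courses as treatment time, which lowers RDI and creates a long therapy delay

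*SAP*

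**What the plan says.** Protocol 7.1.2.1 provides for a second course after treatment has been stopped: "One reinitiating course of treatment at the same dose and schedule and treatment duration up to 24 months is allowed". It covers participants in SD, PR or CR at discontinuation who later progress, and participants stopped for an AE that has since resolved or is well managed.

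SAP Section 13 pools the two courses: "Data collected during the treatment reinitiation phase will be included in the summary" statistics, and they are also listed. Its derivations are:

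- Duration in weeks is the date of the last dose minus the date of the first dose, plus 14 days, divided by 7.
- Cumulative dose "is the sum of the actual dose that the participants received during the study".
- DI is cumulative dose divided by half the duration in weeks, that is, per two-week cycle.
- RDI is 100 times DI over planned dose: "Where the planned dose is 1200 mg/cycle". It is summarized as a continuous variable and in three categories: below 80%, 80% to 90%, above 90%.
- Therapy delay is the interval between consecutive infusion start dates minus 14 days. "If the result is > 0 day, then this will be classed as a delay". The longest delay per participant is grouped as none, 1-2, 3-8, 9-15 and 16 days or more.

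No text in Section 13 or Section 9.11 subtracts the time between courses or exempts the first reinitiation infusion from the delay rule. SAP Section 6.1 keeps exposure and compliance in the restricted analysis for the abbreviated report.

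**The concern.** DI and RDI are meant to show how closely dosing followed the planned schedule while the participant was on treatment. Between the end of the first course and the start of the second, the participant has been discontinued and no dose is due. The single-span duration still puts that time in the denominator, while the numerator holds only the doses given. A participant who received every due dose in both courses can then appear in the lowest RDI category, and the stop between courses appears in the delay table as a late infusion. Treatment duration is inflated in the same way. At stake is the accuracy of the descriptive exposure summaries for this subgroup.

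**Working it through.** **Check on an uninterrupted course.** The plan states no RDI result to reproduce, but its formula should return the planned 1200 mg/cycle when dosing is perfect. Twelve doses exactly 14 days apart give a duration of 24 weeks, a cumulative dose of 12 × 1200 = 14,400 mg, DI = 14,400 / 12 = 1200 mg/cycle, RDI = 100% and no delay. The formula works for a single course.

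**One reinitiated participant.** Assume 13 on-schedule doses, 26 weeks off drug after the last 14-day cycle of the first course, then 13 more on-schedule doses. The dose counts and the gap are assumptions; the documents give neither.

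- Duration as written: 26 + 26 + 26 = 78 weeks.
- Cumulative dose: 26 × 1200 = 31,200 mg.
- DI: 31,200 / 39 = 800 mg/cycle.
- RDI: 100 × 800 / 1200 = 66.7%, in the below-80% category.
- Delay at the first reinitiation infusion: 26 × 7 = 182 days, in the category of 16 days or more.

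Summing by course gives 26 + 26 = 52 weeks, DI = 31,200 / 26 = 1200 mg/cycle, RDI = 100% (above-90% category) and no delay.

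**General form.** For K on-schedule doses in total and a gap of g weeks, duration as written is 2K + g, so RDI = 100 × 2K / (2K + g). RDI falls below 90% when g > 2K/9 and below 80% when g > K/2. For K = 24 these limits are 48/9 = 5.3 weeks and 12 weeks. On-drug RDI is 100% in every cell below:

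| Doses (first + second course) | 4-week gap | 12-week gap | 26-week gap | 52-week gap |
|---|---|---|---|---|
| 6 + 6 | 85.7% | 66.7% | 48.0% | 31.6% |
| 12 + 12 | 92.3% | 80.0% | 64.9% | 48.0% |
| 26 + 12 | 95.0% | 86.4% | 74.5% | 59.4% |

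The same gaps are scored as delays of 28, 84, 182 and 364 days.

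**Alternative reading.** Suppose the last dose meant the end of the first course, with cumulative dose still study-wide. The 13 + 13 example would then give 31,200 / 13 = 2400 mg/cycle and RDI 200%, so that reading does not work either. SAP Section 15.2.1 also takes the last dose of a reinitiated participant from the second course, and Section 9.8 uses one on-treatment period across both courses. The single-span reading is the natural one.

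**Visit window (secondary).** Protocol Table 1 allows ±3 days per treatment visit. Infusions 15, 16 or 17 days after the previous one score delays of 1, 2 or 3 days. On a fixed visit calendar, one infusion 3 days early followed by one 3 days late gives an interval of 14 + 3 + 3 = 20 days, a 6-day delay with both visits in window. The documents contain no visit-timing data, so 100,000 participants with 5 infusions, all in window, were simulated under assumed timing. The share with at least one delay was 98.5% with timing uniform on a fixed calendar, 89% with timing uniform around the previous infusion, and 48% with 80% of infusions exactly on the day.

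**The case against.** The strongest reply is that pooling is deliberate and transparent. Protocol 9.4 leaves post-reinitiation data to the analysis plan, and the SAP pools consistently. Reinitiation infusions are flagged in the dosing listing. Section 10.1 counts reinitiated participants and lists the dates of both courses, so a reader could recompute. This stands as mitigation, but the summary tables would still carry the distorted values.

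For participants stopped for an AE, time off drug might be regarded as a real loss of dose intensity. That is arguable, but the SAP does not say it intends this, and the formula treats every reason for stopping alike.

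A reader might infer more than the documents support:

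- *RDI is wrong in general.* It is not. The gap error is confined to reinitiated participants, and the formula is right for an uninterrupted course.
- *Responders are the ones who look under-dosed.* Protocol 7.1.2.1 also admits participants with SD and those stopped for AEs, and the mix is not given.
- *The gap is a scheduled stop.* Under Protocol 4.1 only confirmed CR carries a time limit, which is 24 months after confirmation and can be extended; SD and PR continue until progression or another stopping criterion.
- *The delay rate is invalid and touches nearly everyone.* Counting any interval over 14 days is an explicit, reproducible convention, and no text defines a delay as outside the visit window. The graded categories separate 1-2 days, although day 3 is pooled with 3-8. The simulated shares depend wholly on assumed timing.
- *Compliance and tolerability cannot be assessed.* Protocol 6.4 defines noncompliance separately. SAP Sections 13 and 15.1.2 report infusion interruptions, rate reductions and the TEAEs leading to interruption or discontinuation.

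**Conclusion.** The point holds for reinitiated participants only. As written, SAP Section 13 overstates their treatment duration, understates their DI and RDI, and scores the between-course gap as a therapy delay. In the 13 + 13 example duration is 78 weeks instead of 52, and RDI moves from the top category to the bottom one. For a total of 24 doses, a gap of a few weeks is enough to change the category. These sizes rest on assumed gaps and on-schedule dosing. The number of reinitiated participants is not stated, so the effect on the overall tables cannot be given. The tables are descriptive, on the Safety Analysis Set, and ORR is untouched. This is a minor correction. The visit-window matter is a reporting choice worth improving, not an error in the definition.

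**What to change.** In SAP Section 13, define duration as the sum over courses of (last dose − first dose + 14) / 7, with first and last dose taken within each course. Base DI and RDI on that sum, and exclude the interval between courses from the delay derivation. If the sponsor wants off-drug time after an AE stop to count against dose intensity, the SAP should say so and show it separately.

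Optionally, add a row for delays outside the protocol's ±3-day window, measured against the scheduled visit date. A cut-off on the interval at more than 17 days would not do: on a fixed calendar it would still count the 20-day in-window interval shown above.

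The cost is a few lines of SAP text and small programming changes. No new data are needed, because the first and last dates of the reinitiation course are already among the listed items in Section 10.1.
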